3.6.1.1 Recurrence-free Survival (RFS)

For Part 1 analysis, the non-parametric Kaplan-Meier method will be used to estimate the RFS curve in each treatment group. The treatment difference in RFS will be assessed by the stratified log-rank test. A stratified Cox proportional hazard model with Efron's method of tie handling will be used to assess the magnitude of the treatment difference (ie, HR) between the treatment arms. The HR and its 95% CI from the stratified Cox model with Efron's method of tie handling and with a single treatment covariate will be reported. Kaplan-Meier estimates and the corresponding 95% CIs at specific follow-up time-points will be provided for RFS. The stratification factors used for randomization (see protocol Section 6.3.1.1 – Stratification) will be applied to both the stratified log-rank test and the stratified Cox model.

For the primary RFS analysis, the true date of event will be approximated by the date of the first assessment at which event is objectively documented. Participants who do not experience an event at the time of analysis will be censored at the last disease assessment date.

Since disease assessment is performed periodically, events such as disease recurrence and metastatic disease recurrence can occur any time in the time interval between the last assessment where the event was not documented and the assessment when the event is documented. In order to evaluate the robustness of the RFS endpoint, a sensitivity analysis with a different set of censoring rules will be performed. The sensitivity analysis is the same as the primary analysis except that events after 2 consecutive missed disease assessments or after new anti-cancer therapy if any should be censored at last disease assessment prior to the earlier date of ≥ 2 consecutive missed disease assessments and new anti-cancer therapy. The censoring rules for primary and sensitivity analyses of RFS are summarized in [Table 1](#).

Table 1 Censoring Rules for Primary and Sensitivity Analyses of RFS

Situation	Primary Analysis	Sensitivity Analysis
Recurrence or death documented after ≤ 1 missed disease assessment, and before new anti-cancer therapy, if any	Event at earliest date of documented recurrence or death	Event at earliest date of documented recurrence or death
Recurrence or death documented immediately after ≥ 2 consecutive missed disease assessments or after new anti-cancer therapy, if any	Event at earliest date of documented recurrence or death	Censored at last disease assessment prior to the earlier date of ≥ 2 consecutive missed disease assessment and new anti-cancer therapy, if any
No recurrence and no death; and new anticancer treatment is not initiated	Censored at last disease assessment	Censored at last disease assessment
No recurrence and no death; new anticancer treatment is initiated	Censored at last disease assessment	Censored at last disease assessment before new anticancer treatment

As indicated in Section 3.4.1.1, new primary melanomas will not be counted as RFS events for the primary RFS analysis. A sensitivity analysis to include new primary melanomas as RFS events will be performed. Additional supportive unstratified analyses may also be provided.

3.6.1.2 Distant Metastases-free Survival (DMFS)

Non-parametric cumulative incidence curves will be used to estimate the ‘time to metastatic disease’ curves. The treatment difference in risk for metastatic disease will be assessed by the stratified log-rank test. A stratified Cox proportional hazard model with Efron’s method of tie handling will be used to assess the magnitude of the treatment difference (ie, the HR). The HR and its 95% CI from the stratified Cox model with a single treatment covariate will be reported. The stratification factors used for randomization will be applied, as stratification factors used for analysis, to both the stratified log-rank test and the stratified Cox model. Participants without documented metastatic disease diagnosis will be censored at the date of their last disease assessment.

3.6.1.3 Overall Survival (OS)

The non-parametric Kaplan-Meier method will be used to estimate the survival curves. The treatment difference in survival will be assessed by the stratified log-rank test. A stratified Cox proportional hazard model with Efron’s method of tie handling will be used to assess the magnitude of the treatment difference (the HR). The HR and its 95% CI from the stratified Cox model with a single treatment covariate will be reported. The stratification factors used for randomization (See protocol Section 6.3.1.1 – Stratification) will be applied to both the stratified log-rank test and the stratified Cox model. Kaplan-Meier estimates and the

corresponding 95% CIs at specific follow-up time-points will be provided for OS. Participants without documented death at the time of the analysis will be censored at the date of the participant was last known to be alive.

Additional supportive unstratified analyses may also be provided.

3.6.1.4 Time to subsequent therapy (TTST)

The non-parametric Kaplan-Meier method will be used to estimate the distribution curve in each treatment group. 95% CIs for the median and point estimates at various follow-up times from randomization date will be calculated. Participants who remain alive and do not receive subsequent therapy will be censored on the date of last disease assessments. Pembrolizumab treatment in Part 2 will be included as a subsequent therapy for participants who enter part 2.

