### 1.3.3 Imaging Schedule

	Imaging On Treatment	End of Treatment (EOT)	In Follow-up
Part 1 • Stage IIB and IIC • No evidence of disease at study entry	Every 6 months for one year from randomization	If previous imaging was obtained within 4 weeks prior to the date of discontinuation, imaging at treatment discontinuation is not mandatory.	
 
• Every 6 months in years 2-4 from randomization
 
• Once in year 5 from randomization
 

Part 2 • Stage III • No evidence of disease at entry into Part 2 after loco-regional recurrence	Every 12 weeks for one year from C1D1		
 
• Every 12 weeks in year 2 from C1D1
 
• Every 6 months from years 3-5 from C1D1
 
• Yearly thereafter
 

Part 2 • Stage IV • No evidence of disease at entry into Part 2 after distant recurrence	Every 12 weeks for one year from C1D1		
 
• Every 12 weeks in year 2 from C1D1 *
 
• Every 6 months from years 3-5 from C1D1
 
• Yearly thereafter
 

Part 2 • Stage III/IV • Have unresectable disease at entry into Part 2	Every 12 weeks for two years from C1D1		
 
• Every 12 weeks in year 3 from C1D1
 
• Every 6 months for years 4-5 from C1D1
 
• Yearly thereafter
 

C1D1= Cycle 1 Day 1 of Part 2 Treatment

Note: For participants who stop Part 1 or Part 2 without documented recurrence/progression. Every effort should be made to capture imaging based on Part 1 and Part 2 SoA instructions.

\* Participants who enter Part 2 with history of Stage IV melanoma and have no evidence of disease may be treated for up to 35 cycles and will have year 2 of imaging while on treatment.

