#### **8.11.3.3 Distant Metastases-free Survival Follow-up**

Part 1 participants who start a new anti-cancer therapy with history of local recurrence, or who do not qualify for or do not enter Part 2 therapy will move into DMFS Follow-up until distant metastatic recurrence is identified. Part 2 participants without a history of distant recurrence, with a history of local recurrence who experience a second local recurrence or local progression, or start a new anti-cancer therapy, will move into DMFS Follow-up until distant metastatic recurrence is identified. These participants should be assessed or contacted

by telephone or at an in-person visit approximately every 12 weeks to review disease status, recent imaging and current therapy until participants develop distant metastatic recurrence. Site investigator must collect and review copy of imaging reports, photographs and pathology reports (including imaging and biopsy/pathology assessment done external to site) to update disease status. A central imaging vendor will be used to collect, clean, and hold tumor imaging obtained during the DMFS phase of the study. Images will be collected for possible analysis by BICR. In the event that a participant refuses any further contact, or if a participant is discontinued from the study, the participant can authorize their site investigator to provide updated information about their tumor, anticancer treatment, well-being and overall status updates on their behalf. Radiographic imaging in the DMFS phase may be performed as clinically indicated per local standard of care or following new anticancer therapy imaging schedule and investigator assessments should be reported to the Sponsor. Information regarding post-study anti-cancer treatment will be collected if new treatment is initiated.

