### 9.6.1.4 Summary of Statistical Methods for Efficacy

Table 9 summarizes the primary analysis approach for primary and secondary efficacy endpoints. Sensitivity analysis methods are described above for each endpoint as applicable.

Methods related to exploratory objectives (and supportive analyses including TTST and PRFS2) will be described in the sSAP.

The strategy to address multiplicity issues with regard to multiple efficacy endpoints, multiple populations, and interim analyses is described in Section 9.7 – Interim Analyses and in Section 9.8 – Multiplicity.

Table 9 Analysis Strategy for Key Efficacy Endpoints

Endpoint/Variable (Description, Time Point)	Statistical Method †	Analysis Population	Missing Data Approach
Primary Hypothesis 1			
RFS	Test: Stratified log-rank test Estimation: Stratified Cox model with Efron’s tie handling method	ITT	See Table 8 for censoring rules
Secondary Hypothesis 2			
DMFS	Test: Stratified log-rank test Estimation: Stratified Cox model with Efron’s tie handling method	ITT	Censored at last known disease evaluation
Secondary Hypothesis 3			
OS	Test: Stratified log-rank test Estimation: Stratified Cox model with Efron’s tie handling method	ITT	Censored at last known alive date
† Statistical models are described in further details in the text. For stratified analyses, the stratification factors used for randomization will be used as stratification factors for analysis.			

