3.3.3 Exploratory Objectives

- 1) **Objective:** To compare average change from baseline during the adjuvant treatment period (up to 21 days after last administration) in global quality of life between the 2 treatment arms using the European Organization for Research and Treatment of Cancer Quality of Life Questionnaire (EORTC QLQ-C30) global health status/QoL scale.
- 2) **Objective:** To compare average change from baseline after the adjuvant period (from 21 days after last administration) in global quality of life between the 2 treatment arms using the EORTC QLQ-C30 global health status/QoL scale.
- 3) **Objective:** To characterize health utilities using the EuroQoL-5 Dimension Questionnaire (EQ-5D-5L) healthy utility scores.
- 4) **Objective:** To compare the time to subsequent therapy (TTST) between treatment arms.
- 5) **Objective:** To compare Progression/recurrence-free Survival 2 (PRFS2) between treatment arms.
- 6) **Objective:** To identify molecular (genomic, metabolic, and/or proteomic) biomarkers that may be indicative of clinical response/resistance, safety, pharmacodynamic activity, and/or the mechanism of action of pembrolizumab.

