3.4.1.3 Tertiary/Exploratory Efficacy Endpoints

Time to Subsequent Therapy (TTST)

Time to subsequent therapy is defined as time from randomization to the date of first subsequent therapy (eg, surgery, radiation therapy, antineoplastic therapy) or death (whatever the cause) whichever occurs first.

Progression-free survival 2 (PRFS2)

Progression/recurrence-free Survival 2 is defined as the time between the date of randomization and the earliest of the following:

- date of 1st disease progression per RECIST1.1 beyond the initial unresectable disease recurrence (unresectable local-regional disease recurrence or unresectable distant metastatic disease recurrence);
- date of 2nd recurrence in Participants without evidence of disease after surgery of a resectable 1st recurrence (resectable local regional recurrences or resectable distant metastatic disease recurrence);
- date of death.

3.4.1.4 Exploratory Endpoints Associated with Protocol Part 2

Progression-Free Survival

Progression-free survival (PFS) is defined as the time from the date of 1st dose in Part 2 to the first documented disease progression or death due to any cause, whichever occurs first.

The following analyses will be done for Part 2.

- PFS per RECIST 1.1 assessed by investigators
- PFS per iRECIST assessed by investigators.

Objective response rate

Objective response rate (ORR) is defined as the proportion of the participants in the analysis population who have a confirmed complete response (CR) or partial response (PR).

The following analyses will be done for Part 2.

- ORR per RECIST 1.1 assessed by investigators
- ORR per iRECIST assessed by investigators.

Duration of Overall Response (DOR)

For participants who demonstrated CR or PR, response duration is defined as the time from first documented evidence of CR or PR until disease progression or death due to any cause, whichever occurs first.

The following analyses will be done for Part 2.

- DOR per RECIST 1.1 assessed by investigators
- DOR per iRECIST assessed by investigators.

Overall Survival (OS)

For Part 2, overall survival is defined as the time from the date of 1st dose in Part 2 to death due to any cause.

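### TTST is censored at an undefined last disease assessment while later therapies and deaths still count, and no test or effect measure is named for the TTST and PRFS2 comparisons

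*SAP*

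**What the plan says.** SAP 3.4.1.3 defines TTST as "time from randomization to the date of first subsequent therapy (eg, surgery, radiation therapy, antineoplastic therapy) or death (whatever the cause) whichever occurs first". SAP 3.6.1.4 gives the censoring rule: those still alive who have had no subsequent therapy "will be censored on the date of last disease assessments". OS, in SAP 3.6.1.3, is instead censored when the participant was last known to be alive.

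The Part 1 schedule (Protocol 1.3.1) records post-study anticancer therapy status at every post-treatment visit type: safety follow-up, follow-up visits, DMFS follow-up and survival follow-up. Protocol 8.11.4 lets the sponsor request a vital-status update before any interim or final analysis. Part 1 scans are six-monthly to year 4, then "Once in year 5 from randomization" (Protocol 1.3.3). Clinic visits go on yearly from year 6 after end of treatment.

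On the comparison, SAP 3.3.3 states the objective "To compare the time to subsequent therapy (TTST) between treatment arms", with a parallel objective for PRFS2. Protocol 9.6.1.4 defers the method: "Methods related to exploratory objectives (and supportive analyses including TTST and PRFS2) will be described in the sSAP". SAP 3.6.1.4 then says "The non-parametric Kaplan-Meier method will be used to estimate the distribution curve in each treatment group", with confidence intervals for the median and for point estimates. SAP 3.6.1.5 does the same for PRFS2. SAP Table 4 covers only RFS, DMFS and OS.

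**The concern.** Starting a therapy and dying are not findings of a disease assessment. A participant who dies or starts therapy after the last assessment is counted at the true date. A participant known on that same date to be alive and untreated is moved back to the earlier assessment. Only event-free people leave the risk set early, so the curve is pushed down in both arms. The direction follows from the rule and needs no model.

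The size depends on what a disease assessment is, and the documents can be read two ways:

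- **Scans only.** The disease evaluation block of the Part 1 schedule lists tumor imaging, pathology report and lesion photograph, and puts the directed physical examination under safety procedures. Protocol 4.1 and 8.2.1.2 use the term in the context of imaging.
- **Visits as well.** Protocol 4.1 accepts recurrence found by examination and biopsy, 8.3.1.2 has the directed examination look for local and regional recurrence, and 8.11.3.2 describes efficacy follow-up visits as monitoring disease status.

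The second issue is that an objective worded as a comparison has no stated estimator of the difference between arms.

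**Working it through.** **No stated figure to reproduce.** The plan gives no number for TTST. The HR borrowed below can be checked against the RFS power: Φ(√179/2 × |ln 0.60| − 1.96) = Φ(3.417 − 1.960) ≈ 0.927, against about 92% stated.

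**Inputs (SAP 3.9).** Control RFS of 68% at 60 months with a 50% long-term plateau; HR 0.60; 16-month accrual; 4.7% yearly drop-out. *Assumption:* TTST follows this RFS curve in promotion-time cure form, S(t) = exp{−θ(1 − e^(−λt))}. Then θ = −ln 0.50 = 0.693 and λ = −ln(1 + ln 0.68/θ)/60 = 0.01355 per month. This gives S(24) = 0.825, S(60) = 0.680, S(84) = 0.624 and S(120) = 0.573. The pembrolizumab curve is S(t)^0.60.

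**Simulation.** 400 trials, 477 per arm. Events count up to the cutoff or drop-out. Event-free participants are censored (a) at the cutoff or drop-out, so that status is fully known, (b) at the last clinic visit or scan, or (c) at the last scheduled scan. Mean Kaplan-Meier estimates, placebo:

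| Cutoff (month) | Time (months) | True | (a) Status known | (b) Visit or scan | (c) Scan only |
|---|---|---|---|---|---|
| 33 | 24 | 0.825 | 0.825 | 0.821 | 0.810 |
| 48 | 36 | 0.765 | 0.766 | 0.760 | 0.758 |
| 60 | 48 | 0.718 | 0.718 | 0.712 | 0.710 |
| 108 | 60 | 0.680 | 0.681 | 0.679 | 0.677 |
| 108 | 84 | 0.624 | 0.625 | 0.622 | 0.198 |
| 180 | 84 | 0.624 | 0.626 | 0.624 | 0.387 |
| 180 | 120 | 0.573 | 0.575 | 0.571 | 0.151 |

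Pembrolizumab shows the same pattern. At 24 months (month-33 cutoff) it reads 0.887 under (b) and 0.880 under (c), against 0.891 true. At 84 months (month-180 cutoff) it reads 0.753 and 0.460, against 0.754 true. Under (c) the gap between arms at 84 months therefore shrinks from 0.754 − 0.624 = 0.130 to 0.460 − 0.387 = 0.073.

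**Why the tail collapses under (c).** After month 60 every participant still in the risk set is one who later has an event. The curve becomes S(60) multiplied by the share of post-60 events that occur after t. Ignoring drop-out and ending at month 168 (true value 0.537):

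- 84 months: 0.680 × (0.624 − 0.537)/(0.680 − 0.537) = 0.680 × 0.087/0.143 = 0.414
- 120 months: 0.680 × (0.573 − 0.537)/0.143 = 0.680 × 0.036/0.143 = 0.171

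The simulated 0.387 and 0.151 are close; drop-out, which this formula ignores, thins the later events and lowers them a little.

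**Limit of these sizes.** The tabled times lie at least 9 months before the cutoff. At the extreme right edge any lagged censoring does worse. At 48 months with a month-48 cutoff, (b) reads 0.535 and (c) 0.129 against 0.718 true, but almost nobody is at risk there.

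**Sensitivity.** A variant adds an other-cause death rate of 0.059 per 10 years and therapy one month after detected recurrence. Both values are assumptions and not in the documents. At 36 months (month-48 cutoff) it reads 77.5% by visit and 77.3% by scan against 78.7% true. At 72 months (month-108 cutoff) it reads 39% by scan against 64% true.

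**The case against.** Several points on the other side stand.

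- **The 12-weekly contacts.** A reader might infer that a stream of 12-weekly contacts is being discarded. Protocol 8.11.3.3 does say "Information regarding post-study anti-cancer treatment will be collected if new treatment is initiated", but DMFS and survival follow-up are entered after recurrence, new therapy or distant metastases, so most of those participants have already had a TTST event. Event-free Part 1 participants are seen at efficacy follow-up visits every 12 weeks, then six-monthly, then yearly. For them the discarded time comes from those visits, if they are not assessments, and from vital-status updates.
- **The large figures.** A reader might infer that TTST will be wrong by 20 points or more. That needs the scan-only reading and times beyond year 5. The visit reading is equally open, and on it the bias is negligible for an exploratory curve. The SAP amendment supports the RFS interim analysis at about month 33, and no later TTST analysis is scheduled by name.
- **The comparison.** A reader might infer that no comparison is planned. SAP 3.6.1 promises nominal p-values for other efficacy analyses and applies the randomization strata to all stratified analyses. Its descriptive-only limit concerns Part 2 endpoints. Only the named test and the effect estimate are missing.

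One argument is weaker than it looks. RFS uses the same censoring term, and a scan-only reading would harm RFS too, which might seem to rule that reading out. But both planned RFS analyses (about months 33 and 48) fall before scheduled scans end, so it would do no such harm there.

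**Conclusion.** The point holds as a minor one. The censoring rule does not match the TTST event, and the bias is downward in both arms whatever the event rate. Its size is about 0 to 1 point if clinic visits count as assessments and up to about 1.5 points before year 5 if only scans count. On the scan-only reading it is severe after year 5. These sizes assume that TTST follows the planned RFS curve, that events after the last assessment become known, and that estimates are read away from the right edge of follow-up. If events after the last visit stay unknown, the bias on the visit reading is smaller still.

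The documents do not establish that the scan-only reading is intended, so the large tail figures show what the undefined term allows and are not a forecast. For TTST and PRFS2, what is missing is a named test and effect measure. Both endpoints are exploratory and outside the alpha plan.

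**What to change.** In SAP 3.6.1.4, censor at the last date on which the participant was known to be alive and free of subsequent therapy, meaning the last visit or contact with therapy status recorded. Apply one data cutoff to events and censoring. The OS rule cannot simply be copied, because a vital-status check need not establish therapy status, so therapy status should be asked alongside any vital-status update before a lock. With status complete to the cutoff, the simulated estimates are within about 0.3 points of truth. If status is known only at 12-weekly contacts, a small bias remains (0.818 against 0.825 at 24 months, month-33 cutoff). Against the visit reading, the main gain is a rule that no longer depends on an undefined term.

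In SAP 3.6.1.4 and 3.6.1.5, add the stratified Cox HR with 95% CI and a nominal stratified log-rank p-value, the methods already used for DMFS and OS.

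The cost is a few SAP sentences, minor programming and one added question at vital-status updates. Therapy status is already collected at visits.

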3.6.1.5 Progression-free survival 2 (PRFS2)

The non-parametric Kaplan-Meier method will be used to estimate the distribution for PRFS2. 95% CIs for the median and point estimates at various follow-up times from randomization date will be calculated. Participants who remain alive and whose disease has not recurred, or disease has recurred, but subsequent disease progression or recurrence has not occurred, will be censored on the date of last disease assessments.

3.6.1.6 Progression-Free Survival (PFS)

For Part 2, the non-parametric Kaplan-Meier method will be used to estimate the PFS distribution. 95% CIs for the median PFS and PFS point estimates at various follow-up times from first day of study treatment in Part 2 will be calculated.

Since disease progression is assessed periodically, progressive disease (PD) can occur any time in the time interval between the last assessment where PD was not documented and the assessment when PD is documented. The true date of disease progression will be approximated by the earlier of date of the first assessment at which PD is objectively documented per RECIST 1.1 by investigators and the date of death. Death is always considered as a PD event. Sensitivity analyses will be performed based on iRECIST by investigator's assessment.

For the analysis of PFS, any participant who experiences an event (PD or death) immediately after 2 or more missed disease assessments will be censored at the last disease assessment prior to the missed visits. In addition, any participant who initiates new anti-cancer therapy prior to documented progression will be censored at the last disease assessment prior to the initiation of new anti-cancer therapy. Participants who do not start new anti-cancer therapy and who do not experience an event will be censored at the last disease assessment. If a subject meets multiple criteria for censoring, the censoring criterion that occurs earliest will be applied. The censoring rules for PFS analyses are summarized in [Table 2](#).

Table 2 Censoring Rules for Analyses of PFS

Situation	Date of Progression or Censoring
PD or death documented after ≤ 1 missed disease assessment, and before new anti-cancer therapy, if any	Progressed at date of documented PD or death
Death or progression after ≥ 2 consecutive missed disease assessments without further valid non-PD disease assessments or after new anti-cancer therapy	Censored at last disease assessment prior to the earlier date of ≥ 2 consecutive missed disease assessment and new anti-cancer therapy, if any
No PD and no death; and new anticancer treatment is not initiated	Censored at last disease assessment
No PD and no death; new anticancer treatment is initiated	Censored at last disease assessment before new anticancer treatment
PD = progressive disease	

